9 ETHICAL CONSIDERATIONS

9.1 General considerations

This study should be developed in accordance with what is established in this protocol and with the standards of Good Clinical Practice (GCP), as described in:

- Harmonized Tripartite Rules of the ICH for Good Clinical Practice 1996. Directive 91/507 /EECC: Good Clinical Practice Standards for testing of medical products in the European Community.
- Declaration of Helsinki in its latest revised version (Fortaleza, 2013) (Annex-1)

The study will only begin after having obtained in writing the authorization of the Research Ethics Committee of the Univeristario de Bellvitge Hospital (Hospitalet de Llobregat, Barcelona) that acts as reference center (CEIm).

With the exception of those emergency situations, changes or deviations from the protocol will not be allowed without documented approval.

The CEIm must be informed of possible changes and will approve in writing any change or deviation that may increase the risks of the subject and / or adversely affect the rights of or the validity of the investigation. This stipulation does not apply to those changes that are made to reduce the inconvenience or avoid risks to the subjects and to the changes that affect the administrative aspects of the study (eg, change of monitor).

9.3 Information sheet and informed consent

The investigator is responsible for ensuring that the patient (and / or legally authorized representative) understands the risks and benefits of their participation in the study, answering any questions that may arise during the study, and sharing any timely new information that could influence the decision to continue their participation in the study.

The patient (or his legal representative) will be informed of the characteristics of the clinical trial, verbally and in writing, through the INFORMATION SHEET.

Finally, after being fully informed of the implications and restrictions of the protocol, having answered their questions and before starting the study, the patient will be asked to give an INFORMED CONSENT in writing. The patient information sheet model and the informed consent form are attached as an annex to this protocol. By signing and dating the informed consent form, the subject declares their voluntary participation and their intention to comply with the Study Protocol and the Investigator's Instructions and respond to issues that arise throughout the Study.

The subject will keep the information sheet throughout the study, with all the relevant study information, including the researcher's contact. The researcher must keep the informed consent in the study file.

9.4 Review of the Ethics Committee

This protocol will be approved by the Research Ethics Committee of the Hospital Universitario de Bellvitge (Hospitalet de Llobregat, Barcelona), which will act as a reference committee for the rest of the participating centers.

Any member of the Ethics Committee, who has a direct relationship with this study as an investigator or as a center staff, will abstain from voting to approve the protocol.

All changes to the protocol will be specified in the form of an amendment. The method of realization of the amendments will follow the standardized procedures according to RD 1090/2015, of December 4.

9.5 Confidentiality of the data

By signing the protocol, the researcher undertakes to keep all the information provided by the Promoter in strict confidentiality and that he will insist on the maintenance of the same by his team and the CEIm. The study documents provided by the Promoter (protocols, researcher's manual, CRDs and other materials) should be conveniently stored in the investigator's file, to ensure confidentiality. The researcher will in turn ensure that the researcher's file is kept in accordance with the conditions specified in Directive 2001/20 / EC.

The researcher will ensure the maintenance of the anonymity of the participating subjects. Both in the CRDs and in other EC documents, the subjects can not be identified by their names but by an identification code. The researcher will keep a record of the inclusion of subjects that shows the codes, names and contact information.

The information provided to the researcher by the Promoter may not be disclosed to third parties without the direct written authorization of the former, except to the extent necessary to obtain the informed consent that they wish to participate in this EC.

The information obtained will be considered strictly confidential based on Organic Law 15/1999, of December 13, on the Protection of Personal Data. (BOE No. 298, of 14-12-1999, pp. 43088-43099) and its development regulations. The collection of medical data will be done in accordance with Recommendation n. R (97) 5 of 13 February 1997, of the Committee of Ministers of the Council of Europe to the Member States on the Protection of Medical Data.

9.6 Records in CRD and reports

The researcher must ensure the accuracy, completeness and timeliness of the data communicated to the promoter in the CRD and in all requested reports. The data will be registered in an online CRD to which only the researcher will have access through a user and a personal and non-transferable password. All the data obtained will be stored in an electronic file of restricted access to the staff of each center and of which the principal investigator will be responsible.

Any change or correction to a CRD should be requested to the CRO in charge of monitoring, Clever Instruments S.L., contacting the person in charge of the data management designated by the promoter of the study. Changes must be documented and the researcher must keep records of changes and corrections.

Researchers or the institution must maintain the EC documents, as required by the applicable regulations. The investigator or the institution must take measures to prevent accidental or premature destruction of such documents.

Upon request of the monitor, auditor, CEIC or regulatory authority, the investigator / institution must have available all records related to the EC.

9.6.1 Monitoring Reports

The promoter or the CRO shall send written summaries of the status of the test to the CEIm annually, or more frequently, if so required by the CEIm.

The promoter or the CRO must provide punctual written reports to the CEIm and, when pertinent, to the institution about changes that significantly affect the development of the trial and / or increase the risk for the subjects. The investigator must supervise and sign these reports.

9.6.2 Security Reports

The promoter must be informed immediately of all serious adverse events, except those that are specified in the protocol or other document. It will be reported quickly, in writing, in detail and in the time periods specified by the promoter in the protocol. These follow-up reports must identify the subjects by means of the codes assigned in the CB and not by the names of the subjects, personal identification numbers and / or addresses.

9.6.3 Premature Termination or Suspension of the Protocol

If the study ends prematurely or is suspended for any reason, the investigator / institution should promptly inform the study subjects, providing appropriate therapy and follow-up. Further:

- If the researcher completes or suspends the study without prior agreement with the promoter, the researcher should inform the institution when appropriate, and the researcher / institution should promptly inform the promoter and the CEI, as well as send an explanation to the promoter and CEI Detailed written explanation of the termination or suspension.
- If the promoter completes or suspends the study, the investigator should promptly inform the institution when appropriate and the investigator / institution should promptly inform the CEI, sending a detailed written explanation of the termination or suspension
- If the CEI withdraws approval of the study, the investigator should inform the institution when appropriate and the investigator / institution should notify the promoter promptly and provide a detailed written explanation.

9.6.4 Investigator's Final Report

At the end of the study, the researcher, when appropriate, should inform the institution. The researcher / institution must provide the CEI with a summary of the results of the study.

9.7 Monitoring

It is established that the development of the study will be followed at regular intervals. The monitoring will be carried out by the monitor (s) designated by the Promoter. Regular contacts will be established between the Monitor / s and the Investigator.

It will be the responsibility of the Monitor to verify compliance with the protocol and the integrity, consistency and reliability of the data entered in the CRDs. For this, the monitor must be able to access the participant's medical history and other documents. The researcher or his collaborators agree to cooperate with the monitor to ensure that the detection of any problem in the course of monitoring is resolved.

Extraordinary audits can be carried out to guarantee the validity of the study data and compliance with the regulations in force.

9.8 Budget of the study

The economic aspects of the study are detailed in the corresponding annex and that supposes a separate document.

9.9 Insurance

As this is a low-level intervention study, it will not be necessary to take out insurance, as long as the individual or collective professional civil liability insurance (or equivalent financial guarantee) of the health center where the clinical trial is carried out covers the damages and damages that participation in the study may cause to patients. Such procedure will be done in accordance with the legislation of RD 1090/2015 (Annex 6: Certificate of the representative of the center / organization for clinical trials of low level of intervention)

10. PREPARATION AND CONSERVATION OF THE PRODUCT

10.1 Conditioning

The product under study (Lit-control®pH Meter and Lit-control®pH Down) must be stored by the researcher in a dry and safe place. Sufficient product will be assigned for the sample calculated in the sample calculation taking into account the initial / theoretical distribution of patients per center and that in the experimental group should be delivered during the baseline product visit for the duration of the entire study.

10.2 Labeling EC sample, products or treatments

Being a double-blinded placebo study, the researcher will deliver a box with no other distinctive than the patient and clinical trial code that will contain the Lit-control®pH Meter device and the Lit-control food supplement. ®pH Down or placebo depending on the arm where the patient is randomized. In addition, Lit-control®pH Down packaging boxes and the placebo will be designed and labeled for the trial to ensure double masking of the study.

10.3 Preservation, dispensation and return

The products provided for the EC should be stored at room temperature in a restricted access area free of extreme environmental conditions. It must be an area that can be closed with limited access to the researcher.

At the reception, an inventory of the shipment must be made; the document must be signed by the researcher or authorized person and a copy will be sent to the Monitor and another to the Investigator's Archive.

The researcher will be responsible for the return of the products, should document any discrepancies in the records of formula stocks.

11 ADVERSE EVENTS

The Adverse Events (AA) produced during the study will be evaluated. An AA is defined as any harmful event in a patient after randomization and during the performance of a study, even if it is considered not to be related to the treatment of the study. In this CE, the AAs in the CRD will be collected and recorded, as long as they are serious (if they cause clinical signs or symptoms and are considered clinically significant).

Diseases or medical conditions that were present before administering the product under study, will only be considered as AA if there is a worsening after the start of the study intervention (any procedure specified in the protocol).

To the extent possible, AAs will be described based on:

- Duration (start and end dates).

- Degree of severity (mild, moderate, severe).
- Relationship with the study medication (suspected / not suspected).
- Action (s) taken to correct it.

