11.1 Types

Any unfavorable and unintended sign (abnormal and clinically significant analytical result), associated or not with the use of drugs, will be assessed as an adverse event.

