11.2 Serious Adverse Events

Information on Serious Adverse Events (AAG) and Unexpected Serious Adverse Reactions (RAGI) with suspected causal relationship with the treatments under study, will be collected and recorded in the notification form of Serious Adverse Events (RD223 / 2004). Such serious adverse events must also be notified to the AEMPS, which will be done from the ESIC and for this the investigator must notify it within 24 hours of its knowledge. Only serious, unexpected AAs related to the treatments under study will be reported to the AEMPS.

AAG or RAGI is considered any adverse event or adverse reaction at any dose:

- Produce death of patients,
- Threatens the subject's life,
- Make necessary the hospitalization of the subject or the prolongation of it,
- Produces disability or permanent or significant disability, or
- Lead to an abnormality or congenital malformation.

The intensity of AA will be classified as mild, moderate or severe. The researcher will record the relationship of the study product with the AA according to the following causality terms:

- Related: the AA follows a reasonable time sequence from the moment of exposure to the product. It can not be explained by the clinical condition of the subject or by the procedures / conditions of the study. AA decreases after discontinuation of the study product and reappears once the study product is re-administered.
- Possibly related: the AA follows a reasonable temporal sequence from the moment of exposure to the product, but it may have been caused by the clinical condition of the subject or by the procedures / conditions of the study.
- Improbably related: the temporal association between the AA and the product of the study is such that it is unlikely that there is any reasonable relationship between them. The relationship is not likely due to other possible explanations.
- Not related: the AA, without a doubt, has been caused by the clinical condition of the subject or by the procedures / conditions of the EC. A reasonable explanation must be given, for example, that the product under investigation or an incompatible temporal relationship has not been consumed.

- Not evaluable: the report that indicates an adverse reaction can not be judged because the information that is counted is insufficient or contradictory, and no extra data can be added or the existing ones can be verified.

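### Section 11 puts adverse events in the CRD only if *serious*, in a sense that 11.2 does not share, and *Related* requires re-administration, so the attributable-event rate may be incomplete or misclassified

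*Protocol*

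**What the plan says.** **Recording.** Protocol section 11 counts any harmful event after randomization as an adverse event, "even if it is considered not to be related to the treatment of the study". It then limits what goes into the CRD: events "will be collected and recorded, as long as they are serious (if they cause clinical signs or symptoms and are considered clinically significant". The attributes to be described for each event include "Degree of severity (mild, moderate, severe" and "Relationship with the study medication (suspected / not suspected".

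Section 11.1 says that an adverse event includes "Any unfavorable and unintended sign (abnormal and clinically significant analytical result), associated or not with the use of drugs".

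Section 11.2 defines serious by outcome: death, threat to life, disability, congenital abnormality, and "Make necessary the hospitalization of the subject or the prolongation of it".

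Section 6.3.4 has the investigator record, at stent removal, the presence of adverse effects, the symptoms the patient noticed while the stent was in place, and stent complications. It states no seriousness limit.

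**Causality.** Section 11.2 adds a five-term scale: "The researcher will record the relationship of the study product with the AA according to the following causality terms". The top term, *Related*, includes the condition "AA decreases after discontinuation of the study product and reappears once the study product is re-administered". The next term, *Possibly related*, describes an event that may have been caused by the patient's condition or by study procedures.

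**Use.** Section 3.2 makes the safety of the supplement a secondary objective. Section 7.4 lists the rate of adverse events attributable to treatment among the end points.

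**The concern.** The word *serious* decides what reaches the database, and one chapter gives it two meanings. If one site applies the gloss in section 11 and another applies the list in 11.2, they will enter different sets of events from similar patients. Neither set is everything that section 11 calls an adverse event.

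An event that is never entered cannot be restored by analysis. This is therefore a matter for the protocol, which itself fixes the collection rule.

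The causality terms affect the events that are entered. If an ordinary suspected reaction fits none of the terms as written, raters must improvise, and the count of attributable events then depends on how each of them does so.

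**Working it through.** The protocol gives no expected adverse-event rate and no recording fraction, so there is no figure to reproduce. The check is a comparison of the text.

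**Step 1: what each section lets in.**

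| Section | What it governs | Filter |
|---|---|---|
| 11, definition | What an adverse event is | Harmful, after randomization; related or not |
| 11, recording sentence | What enters the CRD | *Serious*, glossed as causing signs or symptoms and judged clinically significant |
| 11.1 | What is assessed as an event | Clinical significance, for analytical results |
| 11.2 | What *serious* means | Outcome list |
| 6.3.4 | What is collected at the final visit | No seriousness filter |
| 7.2 and 7.4 | A variable and an end point | Attributability |

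**Step 2: read the filter both ways.**

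- *With the 11.2 meaning*, every event that meets none of the listed outcomes stays out. The mild, moderate and severe grading would then have little use.
- *With the section 11 gloss*, symptomatic and clinically significant events of any grade go in. Events without signs or symptoms, or judged not clinically significant, stay out.
- The gloss and the grading favor the second reading. Even so, the recorded set is smaller than the defined set.

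**Step 3: test the second reading against 11.1.** A clinically significant laboratory abnormality without signs or symptoms is an adverse event under 11.1 but fails the gloss. This shows that the rules conflict, not that many events are lost. The urine test that section 6.3.3 requests is at baseline, and no safety laboratory panel after randomization is scheduled.

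**Step 4: ask what section 6.3.4 recovers.** The adverse-effects item could catch treatment-related effects that section 11 filters out. It is collected at a single visit 3 to 8 weeks after baseline, and it does not lift the section 11 rule. The symptom and complication items are about the stent and have no stated causality rating, so they do not feed an attributable rate directly.

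**Step 5: try the 11.2 causality terms on one event.** Take an event with plausible timing, no other explanation, full information and no re-administration.

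- *Related*: fails, because the event was not seen to reappear on re-administration. No section describes such a step, and section 6.2.3 lists a serious adverse event as a discontinuation criterion.
- *Possibly related*: fails, because it presupposes another possible cause.
- *Improbably related*: fails, because the timing is plausible and nothing else explains the event.
- *Not related*: fails, because no other cause is established.
- *Not evaluable*: fails, because the information is neither insufficient nor contradictory.

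Read literally, no term fits. The notification form in Annex 3 offers a not-applicable box for re-administration, so the protocol's own form does not treat that step as always available.

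**The case against.** The strongest reply is that section 11 explains its word on the spot. On that explanation most clinically relevant events are recorded, and 11.2 uses a separate abbreviation for outcome-based seriousness. The text is visibly a translation, so one loosely used adjective is a likely cause. This stands in large part. A reader might infer that only deaths, hospitalizations and similar outcomes are recorded. The gloss and the severity grading do not support that. What remains is that the wording permits two thresholds and that the wider one still falls short of the definition.

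A reader might also count 11.1, 7.2 and 7.4 as further contradictory recording rules. They are not. Section 11.1 says what is assessed, while 7.2 and 7.4 name a variable and an end point with their own filter. Only section 6.3.4 is a competing collection instruction, and it captures part of what section 11 leaves out.

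On causality, *Related* can be seen as a deliberately strict top category, and the gap below it depends on reading *Possibly related* literally. Section 11 also asks for a suspected or not suspected judgment on each event, and a statistical analysis plan can map the two scales and say which terms count as attributable. The absence of a mapping is therefore no defect in itself. Annex 3 is a form for serious events and does not define the 11.2 scale. What stands is that the protocol, as worded, makes an undescribed step a necessary condition for its highest causality term.

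**Conclusion.** The inconsistency is certain; its consequence is possible but unmeasured. The recording rule in section 11 uses *serious* in a sense that differs from 11.2, and either sense records less than the protocol's definition of an adverse event. The 11.2 causality terms, read literally, leave a common type of event without a category. The attributable adverse-event rate may therefore be under-ascertained or misclassified, and may vary by site.

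The size cannot be derived from the document, and an invented event rate would add nothing. A reader might infer that the treatment comparison is biased. The documents do not support that: treatment codes are assigned within each center at 1:1, the trial is double-blind, and nothing indicates that the filter would act differently by arm. Primary efficacy, the incrustation score, is unaffected.

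The conclusion assumes that sites follow the protocol text and that the investigator's manual, which is not at hand, does not already set one recording rule. The point should be fixed because safety is a named objective, events never entered cannot be recovered, and the remedy is cheap.

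**What to change.** Reconcile sections 6.3.4, 11, 11.1 and 11.2 as follows:

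1. In section 11, record every adverse event in both arms in the CRD, whatever its seriousness, and drop the gloss.
2. Keep the outcome list in 11.2 as the only meaning of *serious*.
3. In section 6.3.4, state that adverse effects reported at the final visit are entered as adverse events under the same rule.
4. Use one causality scale in which re-administration is not a necessary condition for *Related*, and which has a term for an event with plausible timing and no other explanation. This concerns classification only; it takes no position on whether the product should be re-administered.

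Reporting all-cause event rates by arm beside the attributable rate would be useful but is optional.

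The cost is protocol and CRD wording and slightly more data entry per patient. No extra visits or tests are needed.
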